6.12. General Statistical Methodology

This section describes in general terms the statistical models and methods applied.

6.12.1. Statistical methodology for count data

Count data is analyzed assuming data is negative binomially (NB) distributed.

A generalized linear model with NB distribution is assumed.

- T_j denotes the length of observation for subject j.
- Y_j denotes the counts of interest for subject j during t_j.
- $\mu_j \qquad \text{denotes the mean of the NB distribution of } Y_j.$

The mean for the distribution of the ARR for subject j, denoted by μ_j/t_j , is modeled by the following equation:

$$\log(\mu_j/t_j) = \mathbf{x}'_j \mathbf{\theta}$$
, *i.e.*, $\log(\mu_j) = \mathbf{x}'_j \mathbf{\theta} + \log(t_j)$, where

- \mathbf{x}_{j} is the vector denoting study treatments and covariates for subject j
- θ is the vector of unknown fixed-model parameters.

Example SAS code for the NB model with 95% confidence interval (CI) is as follows:

The offset variable used is specified per analysis (e.g., for ARR it is the log-transformed observation time, for total T1 lesions it is the log-transformed number of available MRI scans).

The 'LSMEANS' statement is used to output the mean estimates for each of the treatment arms with 95% Wald CIs).

The 'ESTIMATE' statement is used to output the rate ratio of the treatment effect with 95% Wald CIs for any relevant comparisons.

In the event that the NB model does not converge, a Poisson model is used. For the Poisson distribution, a Poisson regression is conducted with model equation identical to the one for the negative binomial regression. Example SAS code for the Poisson model with 95% CI is as follows:

```
proc genmod data=ADREL;
class Treat;
model COUNTS = Treat / dist=poisson link=log
offset = offset;
lsmeans Treat / cl exp alpha = 0.05;
estimate 'A vs B' " Treat 1 -1/ exp alpha = 0.05;
run;
```

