1.3.2.3 Efficacy in humans

Study AC-058B201 [Olsson 2014] was a prospective, multicenter, randomized, doubleblind, placebo-controlled, parallel-group, dose-finding Phase 2b study, in which efficacy, safety, and tolerability of three doses of ponesimod administered for 24 weeks were investigated in patients with RRMS. A total of 464 patients were randomized (1:1:1:1) to 10, 20, or 40 mg ponesimod as the capsule formulation, or placebo. Study medication was administered orally o.d., with a starting dose of 10 mg o.d. in all ponesimod arms and with uptitration to 20 and 40 mg on Days 8 and 15, respectively. Of the 464 patients randomized in the study, all but two patients (ponesimod 20 mg) received treatment with study drug.

In the ponesimod groups, the mean cumulative number of new T1 gadolinium-enhancing (Gd+) lesions at Weeks 12 to 24 (primary efficacy endpoint) ranged from 1.1 3.5 compared to 6.2 on placebo. In the primary analysis (negative binomial regression analysis on the Per-protocol set with imputation for missing data), a statistically significant effect was demonstrated for each ponesimod dose group. The treatment effect (ratio) versus placebo with ponesimod 10 mg was 0.566 (95% confidence interval [CI]: 0.337, 0.952, p 0.0318), with ponesimod 20 mg 0.170 (95% CI: 0.100, 0.289, p 0.0001), and with ponesimod 40 mg 0.226 (95% CI: 0.133, 0.384, p 0.0001).

A mean reduction of 70% of the cumulative number of new T_1 Gd+ lesions from Week 12 to Week 24 was estimated with the 20 mg dose. Only a minor further increase in the effect was estimated for doses greater than 20 mg.

The results from an interim analysis of study AC-058B201/B202 with cut-off date of 31 March 2019 have shown sustained low rates of MRI and clinical disease activity as well as low rates of relapse and disability accumulation during long-term treatment with ponesimod for up to 9 years. The model- adjusted ARR estimated with ponesimod 20 mg was approximately 0.15.

Study AC-058B301/OPTIMUM was a prospective, multicenter, randomized, doubleblind, active controlled, parallel-group, Phase 3, superiority study. The study was designed

Ponesimod / ACT-128800 / JNJ-67896153 Multiple Sclerosis		EudraCT 2009-011470-15 EDMS-ERI-206617631
Protocol AC-058B202	Confidential	
Version 12		
15 March 2022, page 46/179		

to compare the efficacy, safety, and tolerability of ponesimod 20 mg versus teriflunomide 14 mg in adult patients with relapsing MS over a treatment period of 108 weeks.

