5.3.2.1. ARR up to end of Analysis Period

ARR for confirmed relapses up to the end of the Analysis Period is analyzed for AP3 on the PAS according to the NB model described in Section 6.12.1.

The model includes the number of confirmed relapses in the Analysis Period for each subject as the response variable, treatment as a factor and the logarithm of time in the Analysis Period (years) as an offset variable.

Mean model-based estimates of the ARR by treatment, as well corresponding 95% CIs are derived. In addition, rate ratios together with corresponding 95% CIs are derived for the following comparisons:

- ponesimod 20 mg vs. Ponesimod 10 mg;
- ponesimod 40 mg vs. Ponesimod 10 mg;
- ponesimod 40 mg vs. Ponesimod 20 mg.

The analysis of ARR for confirmed relapses is summarized in a table by treatment:

• Number of confirmed relapses per subject: descriptive statistics;

CONFIDENTIAL – FOIA Exemptions Apply in U.S.

- Number of confirmed relapses per subject: frequency counts and percentages for categories 0, 1, 2, 3, 4, and 5+;
- Total number of confirmed relapses: sum;
- Total time in Analysis Period (subject years): sum;
- Raw ARR: total number of confirmed relapses/total time in Analysis Period;
- ARR estimate and 95% CI from a NB model, together with the dispersion parameter from the model;
- Rate ratios and 95% CIs for the comparisons listed.

ARR for all relapses is analyzed as described above for confirmed relapses

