5.3.2.3. ARR by year

ARR by year for confirmed relapses is analyzed for AP3 on the PAS, as described for ARR up to the end of the analysis period in Section 5.3.2.1 above. A similar analysis for the number of unconfirmed and confirmed (all) relapses will be provided. Mean model-based estimates of the ARR by year and by treatment, as well corresponding 95% CIs are derived. A summary table and a bar chart are produced to present the ARR by year.

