5.3.4.3. CUAL

The cumulative number of CUAL (as defined in Section 5.3.3.3) is analyzed for AP3 on the PAS, as described in Section 5.3.4.1 for the cumulative total number of T1 Gd+ lesions. The logarithm of the time up to the last MRI scan at which T2 was measured in the Analysis Period (years) is used as an offset variable.

The number of CUAL per MRI time window (as defined in Section 5.3.3.2) is summarized descriptively by treatment group, as described in Section 5.3.4.2 for the cumulative number of new or enlarging T2 lesions, and is presented in both a table and a figure for AP3 on the PAS.

Frequency counts and percentages for the categorical number of CUAL in the Analysis Period are presented by treatment group for AP3 on the PAS. The denominator for percentages is the number of subjects with at least one MRI scan at which T2 was measured during the Analysis Period.

All CUAL data is presented in a listing for AP3 on the PAS.

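### The Poisson fallback for a non-converging negative binomial model carries no over-dispersion correction, dispersion check or disclosure rule; the possible error is large for CUAL, modest to moderate for AP3 ARR and small for ARR by year

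*SAP*

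**What the plan says.** SAP 6.12.1 assumes that counts follow a negative binomial distribution, with a log link and a log-time or log-scan-count offset. For inference, "The 'ESTIMATE' statement is used to output the rate ratio of the treatment effect with 95% Wald CIs for any relevant comparisons". The only alternative is the sentence "In the event that the NB model does not converge, a Poisson model is used", followed by "a Poisson regression is conducted with model equation identical to the one for the negative binomial regression". The example code contains "model COUNTS = Treat / dist=poisson link=log", the offset, and the LSMEANS and ESTIMATE lines. It has no scale option and no REPEATED statement.

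Three sets of Final CSR analyses depend on this rule:

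- ARR over AP3, for confirmed and for all relapses (SAP 5.3.2.1). The table is to show "ARR estimate and 95% CI from a NB model, together with the dispersion parameter from the model" and three between-dose rate ratios.
- ARR by year (SAP 5.3.2.3): "Mean model-based estimates of the ARR by year and by treatment, as well corresponding 95% CIs are derived".
- CUAL (SAP 5.3.4.3): "The cumulative number of CUAL (as defined in Section 5.3.3.3) is analyzed for AP3 on the PAS", using the count model described for T1 Gd+ lesions.

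The NB models for cumulative T1 Gd+ and T2 lesions (SAP 5.3.4.1 and 5.3.4.2) were run for the interim report and are not repeated. SAP 6.2.3 says CUAL takes their place.

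**The concern.** The NB and Poisson models share the same mean equation, so the switch removes only the dispersion term. A plain Poisson model sets the variance equal to the mean. If subjects differ in their underlying rates, its Wald limits are too narrow. The trigger is non-convergence alone, which does not show that dispersion is negligible. Nor must a table say that the switch occurred; at most, a reader of the ARR table might notice that the dispersion parameter is absent.

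SAP 6.2.3 records that p-values were removed from the SAP. The 95% intervals are therefore the main statement of uncertainty left for rates and between-dose ratios, and an interval labelled 95% should cover at close to that level.

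**Working it through.** **1. Reproduce a published NB result.** Protocol 1.3.2.3 gives the core-study ratio for new T1 Gd+ lesions, 10 mg versus placebo, as "0.566 (95% confidence interval [CI]: 0.337, 0.952, p 0.0318", with a placebo mean of 6.2 and a highest ponesimod mean of 3.5.

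- SE of the log ratio = ln(0.952/0.337)/3.92 = 0.265.
- Two-sided Wald p = 0.0317, against 0.0318 stated.
- 6.2 × 0.566 = 3.51, which matches the stated mean.

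**2. Plain Poisson on the same data.** Poisson SE = √[1/(n·μ₁) + 1/(n·μ₂)]. NB variance = (1/n)(1/μ₁ + 1/μ₂ + 2k). The true coverage of a nominal 95% Poisson interval is 2Φ(1.96/r) − 1, where r = NB SE / Poisson SE. The per-protocol n is not given. With 464 randomised 1:1:1:1 there are 116 per arm, so n = 80 to 116 is used as the assumed range. The 20 and 40 mg rows use the stated ratios 0.170 (0.100, 0.289) and 0.226 (0.133, 0.384).

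| Dose vs placebo | NB SE | Poisson SE (n = 116 / 80) | r (n = 116 / 80) | Coverage (n = 116 / 80) | Implied k (n = 116 / 80) |
|---|---|---|---|---|---|
| 10 mg | 0.265 | 0.062 / 0.075 | 4.27 / 3.55 | 35% / 42% | 3.85 / 2.58 |
| 20 mg | 0.271 | 0.098 / 0.118 | 2.77 / 2.30 | 52% / 61% | 3.70 / 2.38 |
| 40 mg | 0.271 | 0.087 / 0.105 | 3.11 / 2.59 | 47% / 55% | 3.81 / 2.49 |

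At 10 mg and n = 116 the Poisson interval would be about 0.50 to 0.64 instead of 0.337 to 0.952.

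**3. Cross-check on CUAL itself.** Protocol 1.3.2.3 gives a Phase 3 CUAL ratio of 0.44 (0.36, 0.54), from 1.405 and 3.164 lesions per year over 108 weeks. The SE is ln(0.54/0.36)/3.92 = 0.103. Arm size is not in the documents. For an assumed 300 to 700 per arm, r = 2.5 to 3.9.

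**4. Relapses.** With equal means μ, r = √(1 + kμ). Protocol 1.3.2.3 gives an ARR of about 0.15 at 20 mg, and 1.3.2.4 gives a median exposure of 8.02 years, so the AP3 mean is about 0.15 × 8.02 = 1.2 relapses per subject. By year the mean is about 0.15. The values of k are assumed.

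| k | AP3: r | AP3: coverage | By year: r | By year: coverage |
|---|---|---|---|---|
| 0.25 | 1.14 | 91% | 1.02 | 95% |
| 0.5 | 1.27 | 88% | 1.04 | 94% |
| 1 | 1.48 | 81% | 1.07 | 93% |
| 2 | 1.85 | 71% | 1.14 | 91% |

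As a plausibility check, the Phase 3 ARR ratio of 0.695 (99% limits 0.536, 0.902) gives SE 0.101 and p = 0.0003, as stated. For an assumed 400 to 700 per arm, r is about 1.0 to 1.3. At 300 per arm the stated interval would be narrower than Poisson allows, so that size is excluded.

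**5. When the switch is harmless.** Two arms of 145 (assumed) with equal rates were simulated, 4,000 runs per setting, noting when the estimated dispersion fell to its zero boundary.

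- Relapses by year (mean 0.15): the boundary was reached in 58%, 42%, 29% and 13% of runs at k = 0, 0.25, 0.5 and 1. Poisson coverage in those runs was 94% to 96%.
- Eight-year lesion counts at 1.4 per year: the boundary was never reached at k = 0.25 or above. Overall Poisson coverage was 69% at k = 0.25 and 42% at k = 1.

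**The case against.** The harm needs two things together: NB non-convergence and real over-dispersion. The documents report no convergence failure. The core study produced NB estimates for all three doses, and the T1 Gd+ and T2 NB models were completed for the interim report. The sparse by-year fits, where a dispersion estimate near zero is most likely, are also where plain Poisson does least damage. Where the damage would be large, the benign zero-dispersion route did not occur in the simulation. All of this stands, and it limits severity.

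The core-study figures are only a proxy: a different lesion count, over Weeks 12 to 24, in a per-protocol set with imputation, against placebo. The SAP excludes the placebo period. This also stands, although the Phase 3 CUAL interval points the same way.

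The code is labelled as an example, in a section that describes methods in general terms. However, the text itself names an unqualified Poisson model, and no other section adds a correction.

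A reader might infer that relapse intervals would also be far too narrow. The documents give no dispersion estimate for relapses, and the range in the working is modest to moderate over AP3 and small by year. A reader might also infer that dose differences would be presented as established. All objectives are exploratory, p-values are gone, and the ARR table shows raw rates and the distribution of relapse counts beside the model results.

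**Conclusion.** The gap is real but conditional. SAP 6.12.1 switches to plain Poisson on non-convergence alone, with no variance correction, dispersion check or disclosure. If that happens under real over-dispersion, the 95% intervals will not cover at 95%.

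- CUAL: potentially large. The core T1 Gd+ proxy gives intervals 2.3 to 4.3 times too narrow on the log scale, assuming 80 to 116 per arm.
- ARR over AP3: modest to moderate. Coverage is about 91% to 71% for an assumed k of 0.25 to 2.
- ARR by year: small. Coverage is about 91% to 95% over the same k.
- Failure because dispersion is near zero: coverage close to nominal.

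The probability of a switch under real over-dispersion cannot be estimated from the documents. Severity is low because the analyses are exploratory. The point should not be extended to the T1 Gd+ or T2 models, which the Final CSR does not repeat.

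**What to change.** Keep Poisson as the fallback in SAP 6.12.1, and add one of the following to the text and code:

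- a robust sandwich variance, through a REPEATED statement with the subject as the unit; or
- a Pearson scale that is set to 1 whenever the estimate falls below 1.

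The sandwich variance is the more natural choice, because NB variance is not proportional to the mean and the dose groups may differ in mean. Add a rule that every table using the fallback says so in a footnote.

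The cost is one statement or option and a footnote, with no new data. Intervals become somewhat wider than plain Poisson gives. They barely change when dispersion is near zero, and return to roughly NB width when it is not.

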6.12.2. Statistical methods for time-to-event data

The analysis of time-to-event data are conducted using Kaplan-Meier estimates of events over time (including graphical representation), log-rank tests and Cox proportional hazard models.

6.12.2.1. Kaplan-Meier and (stratified) log-rank test

Estimates of the event rate are obtained from the Kaplan-Meier method using SAS PROC LIFETEST. The graphical representation follows the recommendations from Pocock [Pocock 2002]. Two-sided CIs at specific time points are constructed, with confidence limits calculated using Greenwood's formula for the estimate of the standard error. Median time to event, as well

```
CONFIDENTIAL – FOIA Exemptions Apply in U.S.
```

Statistical Analysis Plan AC-058B202

as 25th and 75th percentiles for each group are provided. The corresponding two-sided CIs are calculated using the method of Brookmeyer [Brookmeyer 1982].

Example SAS PROC LIFETEST code is as follows, where the STRATA statement includes the treatment variable (treat), and the TIME statement includes a variable with times to event (time) and an indicator variable for right censoring (censor) with 1 representing censoring.

```
PROC LIFETEST data= method=km;
TIME survtime*censor(1);
STRAT treat;
run;
```

The stratified log-rank test is conducted with SAS Proc Lifetest where the STRATA statement includes the specified covariates and the GROUP option includes the treatment variable (treat). The TIME statement includes a variable with times to event (time) and an indicator variable for right censoring (censor) with 1 representing censoring.

```
Proc lifetest data= method=KM;
time survtime*censor(1);
strata STRAT COVAR / group=treat;
run;
```

6.12.2.2. Cox proportional hazards model

SAS PROC PHREG is used to estimate the hazard ratio and the CI of the hazard ratio (using Wald-based methods). The Cox regression model can be implemented using the following code:

PROC PHREG data =; CLASS treat; MODEL timeto*censor(1)= treat /risklimits ties=exact; run;

6.13. Study visit and assessment schedule

The following tables: Table 15, Table 16, Table 17 and Table 18 correspond to Tables 1, 2, 3 and 4 in the study protocol. Section numbers in the footnotes refer to the protocol sections.

PERIO DS	Name		Transi tion	Double-blind extension treatment period 1													
	Duration				Extended treatment with ponesimod for up to 96 weeks												
VISITS	Number	11		E 1	E 2	E 3		E 4	E 5	E 6	E 7	E 8	E 9	E 10	E 11	E 12	E 13
	Name	EO T ¹		Randomization			Phone call ²										EOT2 3
	Time	W 24	Day -3 to -1	Day 1	Day 8	Day 15	Day 22	We ek 4	We ek 8	Wee k 12	Wee k 24	Wee k 36	Wee k 48	Wee k 60	Wee k 72	Wee k 84	Wee k 96
	Visit			W 24 (EOT) + up	±1	±1	+1 day	±2	±5	±5	±14	±14	±14	±14	±14	±14	±14
	window			to 3 days	day	day		days	days	days	days	days	days	days	days	days	days
* Informe	ed Consent ⁴	х															
* Inclusio criteria	on/Exclusion	х	х	х													
EDSS / Fu Systems	unctional	х									х		х				х
* Chest X	-ray	х															х
* MRI		х									Х		Х				Х
Concomi medicatio	itant ons	х	х	х	х	х		x	х	х	х	х	х	х	х	х	х
* Physica Examinat	l tion	X5			х	х		x	х	X5	X ⁵	X5	X ⁵	X ⁵	X ⁵	X5	X ⁵
Systolic/ blood pre	/diastolic essure	х		X ⁶	X6	X ⁶		х	х	х	х	х	х	х	х	х	х
* 12-lead	ECG	Х		X ₆	X6	X ₆		Х	Х	х	Х	Х	Х	Х	Х	Х	х
* Echocar	rdiography ⁷	х								х	х		х		х		х
Ophthali examinat	mologic tion ⁸	х						x		х	х		х		х		х
Pulmona tests ⁹	ary function	х			х	х		x	х	х	х		х		х		х
* Hemato chemistry	ology/Blood y	х			х	х		x	х	х	х	х	х	х	х	х	х
* Urinaly:	sis	х			х	Х		Х	Х	х	Х	Х	Х	Х	Х	Х	Х
* Pregnar	ncy Test	х						х	Х	х	х	Х	х	х	х	Х	х
PK Samp	ling ¹⁰	х			х	Х		Х			х		х				х
* Study D Dispensir)rug 1g/Return	X ¹¹		х	X ¹²	X ¹²		x	х	х	х	х	х	х	х	х	х
Adverse	Events	х	х	х	х	х	х	х	х	х	х	Х	х	х	х	Х	х
Serious A Events	Adverse	х	x	х	х	х	х	х	х	х	х	х	х	х	х	х	х

 Table 15:
 Visit and assessment schedule (treatment period 1 – up to 96 weeks)

Table 16:	Visit and assessment schedule (Safety Follow-up for patients discontinuing
	during or at the end of treatment period 1 only

	U		1 1		
PERIODS	Name	EXTENSION SAFETY FOLLOW-UP			
	Duration	30 days			
	Number	E14	E15		
	Name	Follow-up E1	Follow-up E2		
			(EOS2)		
	Time	W96 + 7 days	W96 + 30 days		
	Visit Window	±1 day	±5 day		
EDSS / Fun	ctional Systems		X		
* MRI			X		
Concomita	int Medications	Х	X		
* Physical	Examination	Х	X ⁵		
Systolic/di	astolic blood	Х	X		
pressure					
* 12-lead ECG		Х	X		
Ophthalm	ologic examination ⁸		X		
Pulmonary	r function tests	Х	X		

CONFIDENTIAL – FOIA Exemptions Apply in U.S.

Status: Approved, Date: 20 September 2023

* Hematology/Blood	X	X
chemistry		
* Urinalysis	X	X
* Pregnancy Test		X
Adverse Events	X	X
Serious Adverse Events	X	X

Table 17: Visit and assessment schedule (treatment period 2 and treatment period 3 – up to 540 weeks and Safety Follow-up)

PERIODS	Name	Double-blind extension treatme	ent period 2 / Open-label extension period 3 ¹⁷	EXTE	NSION SAFETY FOLLOW-	UP ¹⁴	
	Duration	Extended treatment v	Extended treatment with ponesimod for up to 540 weeks				
VISITS	Number	P1-P3-P5-P7-P9-P11-P13-P15- P17-P19-P21-P23-P25-P27- P29-P31-P33-P35-P37-P39- P41-P43-P45	P2-P4-P6-P8-P10-12-P14- P16-P18-P20-P22-P24-P26- P28-P30-P32-P34-P36-P38- P40-P42-P44				
	Name			EOT313	FU1	FU2	FU3 (EOS3)
Time		Day 1-Week 24-48-72-96-120- 144-168-192-216-240-264- 288-312-336-360-384-408- 432-456-480-504-528	Week 12-36-60-84-108-132- 156-180-204-228-252-276- 300-324-348-372-396-420- 444-468-492-516	Week 540	8 days after the last dose of study drug	30 days after the last dose of study drug	90 days after the last dose of study drug
	Visit window	±14 days	±14 days	±14 days	±1 day	±5 days	±7 days
EDSS / Function	al Systems ¹⁶	х	x	x		x	х
* Chest X-ray		(X ¹⁵) only at P1		х			
* MRI		(X) only at P1, P5, P9, P13, P17, P21, P25, P29, P33, P37, P41, P45		x		x	
Concomitant m	edications	x	х	х	x x		х
* Physical Exami	nation	(X ⁵), at P37, P41, P45	(X⁵) until P36	X ⁵	х	X ⁵	X ⁵
Systolic/diastolic blood pressure ⁶		х	х	х	х	х	х
* 12-lead ECG ⁶		(X ⁶), at P37, P41, P45	(X ⁶) until P36	х	х	х	
* Echocardiograp	ohy ⁷	(X ⁷) at P37, P41, P45		х			
Ophthalmologic	examination ⁸	(X ⁸), at P37, P41, P45		х		х	
Pulmonary function tests ⁹		(X ⁹), at P37, P41, P45		х	х	х	х
* Hematology/Blood chemistry		x	х	х	х	х	х
* Urinalysis		х	х	х	х	х	х
* Pregnancy Test ¹⁸		Х	X	х		x	
PK Sampling ¹⁰		P7 only	(X) only at P2, P14, P22				
* Study Drug Dis	pensing/Return	Х	Х	х			
Adverse Events		x	х	х	х	х	х
Serious Adverse	e Events	х	х	х	х	х	х

Table 18:	Visit and	assessment schedule	(unscheduled	visits)
-----------	-----------	---------------------	--------------	---------

PERIO DS	Name	UNSCHEDULED VISITS							
	Name	Rela pse	Unscheduled	Re-init	iation ²⁰	Interruption / planned pregnancy	Eligibility for re- initiation / pregnancy	Re-initiation D1 / pregnancy	Re-initiation D8 / pregnancy
VISITS				Day 1 of re- initiatio n	Day 15 of re- initiatio n	Unscheduled visit after drug interruption for planned pregnancy	Unscheduled visit prior to study drug re-initiation after interruption for planned pregnancy	Unscheduled visit for re-initiation of study drug following study drug interruption for planned pregnancy	Unscheduled visit for re-initiation of study drug following study drug interruption for planned pregnancy
	Time	Any day between Day 1 and FU3 (EOS3)		Any day between Day 1 and EOT3		30 days after study drug interruption for planned pregnancy	30 days (±5 days) before study drug re-initiation		

CONFIDENTIAL – FOIA Exemptions Apply in U.S.

Status: Approved, Date: 20 September 2023

JNJ-67896153/ACT-128800 (Ponesimod)

Statistical Analysis Plan AC-058B202

	Visit window	+ 7 days	NA	NA	±1 day	±7 days	NA	NA	NA
EDSS / F	unctional	Х	Х			Х	Х		
Systems ¹	.6								
* Chest X	(-ray								
* MRI			Х			Х	Х		
Concom	itant	Х	Х	Х	Х	Х	Х	X ¹⁹	Х
medicati	ons								
* Physica	al	Х	X ⁵			Х	Х		
Examinat	tion								
Systolic	/diastolic	Х	Х	Х	Х	Х	Х	Х	Х
blood pro	essure ⁶								
* 12-lead	I ECG ⁶		Х	Х	Х	Х	Х	Х	Х
Ophtha	Imologic		Х			Х	Х		
examinat	tion ⁸								
Pulmon	ary		х			Х	Х		
function	tests ⁹								
*			х			Х	Х		
Hematol	ogy/Blood								
chemistr	у								
* Urinaly	sis		Х			Х	Х		
* Pregna	ncv Test ¹⁸		х			Х	X (first	X (first	
							assessment)	assessment)	
* Study D	Drug		Х	Х	Х			X ¹⁹	Х
Dispensi	ng/Return								
Adverse	e Events	Х	Х	Х	Х	Х	Х	Х	Х
Serious	Adverse	Х	х	Х	Х	Х	Х	Х	Х
Events									

Note: The footnotes apply to Table 15, Table 16, Table 17 and Table 18.

*Data are not collected in the CRFs (unless a finding constitutes an AE or SAE), except for body weight (see footnote 5). For MRI and echocardiography only the date of assessment is collected in the CRFs.

- All Week 24 (EOT) assessments of the core study (AC-058B201) must be completed prior to randomization in the extension study. If a
 patient is going to enter the extension study the Visit E1 should be scheduled within 3 days after the Week 24 (EOT) visit of the core study.
 Patients will have to continue using their core study medication every day until and including the day prior to Visit E1.
- 2. Phone call: The site will call the patient for information on health status / adverse events.
- 3. In the event of treatment discontinuation prior to Week 96 (whatever the reason), all assessments planned at Visit E13 (EOT2) must be performed as soon as possible, but no later than 5 days following the date of the last dose of study drug.
- 4. Informed Consent Form of the extension study must be signed by the patient prior to participating in any study-related procedure of the extension study, and prior to continuing using their core study medication on the day of their Week 24 visit of the core study.
- Physical examination must be performed at all study visits until P37, then yearly until P45, inclusive, and at EOT3, FU1, FU2, and FU3. Includes careful skin examination at each visit from E6 until P37, then at P41, P45, EOT3, and at FU2 and FU3. Body weight only at E7, E9, E11, E13, and yearly from P1 to EOT3.
- 6. Blood pressure must be performed pre-dose at all visits. ECG must be performed pre-dose at all study visits until P37, then yearly until Visit P45, inclusive. At the visit when the transition from treatment period 2 (TP2) to treatment period 3 (TP3) will occur, all patients must be monitored at the investigational site for at least 6 hours after dose administration [see Section 3.12.2]. In the event of re-initiation of study drug, blood pressure and ECG must be performed pre-dose (all patients) and hourly (±15 min) for at least 4 hours and up to 12 hours (only mandated for patients with cardiovascular risk factors and at the discretion of the investigator / treating neurologist for patients without cardiovascular risk factors) [see Appendix 5 and Section 3.12.5.3].
- 7. Standard 2D/Doppler echocardiography will assess regional wall abnormalities, aortic valve morphology and function, mitral valve morphology and function, and left ventricular ejection fraction. It will be performed at selected centers with adequate equipment and experience. During TP2 and TP3, echocardiography is performed at every other visit from P1 to P35, yearly from Visits P37 to P45, inclusive, and at EOT3.
- 8. Ophthalmological examination includes best corrected visual acuity, low contrast visual acuity, visual fields, dilated ophthalmoscopy, and optical coherence tomography (OCT) in case of suspicion of macular edema or active uveitis (OCT, only for subjects at risk). During TP2 and TP3, ophthalmologic examination is performed at every other visit from P1 to P35, yearly from Visits P37 to P45, inclusive, at EOT3 and FU2.
- 9. FEV₁ and FVC. Additional unscheduled pulmonary function tests (PFTs) will be conducted in the event of respiratory symptoms (e.g., dyspnea) or decreased lung function (FEV₁ and/or FVC <80% of baseline value) during the course of the study. During TP2 and TP3, PFTs are performed at every other visit from P1 to P35, yearly from Visits P37 to P45, inclusive, at EOT3 and FU visits.

- 10. Plasma sample at trough level (pre-dose).
- 11. Patients will have to continue using their core study medication until and including the day prior to Visit E1.

- 12. Dose uptitration or mock uptitration will take place on Days 8 and 15 during TP1. Study drug re-initiation during TP2 will require only one dose uptitration or mock uptitration on Day 8. Study drug re-initiation during TP3 will require only one dose uptitration on Day 8.
- 13. EOT3 visit has to be performed 1 day after the last study drug intake. For premature discontinuations EOT3 should be performed as soon as possible, but no later than 5 days after the last dose of study drug. Additionally, EOT3 visit has to be performed as soon as possible, but no later than 5 days after the last dose of study drug for patients not enrolling into TP3, or for patients completing study treatment due to availability of commercially available ponesimod [see Section 3.12.3.5]. Commercially available ponesimod may be initiated on the day after last intake of study drug.
- 14. The three Safety Follow-up visits must be performed:
 - following premature treatment discontinuation
 - following treatment discontinuation at EOT3
 - following treatment discontinuation for switching to commercially available ponesimod.
- 15. Patients completing the EOT2 (Visit E13) and having a chest X-ray done at this visit must not repeat the chest X-ray at Visit P1.
- 16. If the patient experiences a confirmed relapse she/he must be made aware by the primary investigator / treating neurologist of the possibility of withdrawal and of switching to standard treatments approved for RRMS. The patient's decision must be recorded in the medical records.
- 17. When feasible, patients will be transitioned from TP2 to TP3 at the earliest visit following approval of protocol version 8 by ECs/IRBs and health authorities and after having signed the revised Informed Consent Form. At this visit, all patients must be monitored at the investigational site for at least 6 hours after dose administration [see Section 3.12.2].
- Women who interrupt the study drug because of planned pregnancy will be exempted from any protocol-mandated pregnancy tests after the first positive pregnancy test and until 30 (±5) days before study drug re-initiation.
- 19. Review and assess contraception methods and total duration of study drug interruption, which should not exceed 81 weeks.
- 20. As described in detail in Appendix 5, patients who miss taking the study drug for four or more consecutive days are required to re-initiate ponesimod treatment using the gradual uptitration scheme. In such cases, there will be one or two visits; one visit on the day of re-initiation (Day 1) for all patients. An additional visit 14 days (±1 day) after the day of re-initiation (Day 15) only mandated for patients with cardiovascular risk factors [see Appendix 5] but may be scheduled for any patient at the discretion of the investigator / treating neurologist.

